1.12.2. Potential Benefits

VRx-3996 combined with valganciclovir may benefit patients by reducing lymphoma volume and/or slowing lymphoma growth. Patients who experience a CR following administration of VRx-3996 and valganciclovir could experience substantial benefit. In patients with symptoms related to the presence of lymphoma, VRx-3996 and valganciclovir may result in a reduction of symptoms.

2. OBJECTIVES

2.1. Primary Objective

- Determine the safety and tolerability of VRx-3996/valganciclovir
- Determine a RP2D of VRx-3996/valganciclovir
- Assess activity based on overall response rate (ORR)

2.2. Secondary Objectives

- Evaluate PK parameters of varying doses of VRx-3996 in capsule form and in tablet form (at RP2D only for tablet form)
- Evaluate PK parameters of varying doses of valganciclovir
- Evaluate time to response (TTR)
- Evaluate duration of response (DoR)
- Determine progression-free survival (PFS) and overall survival (OS)

2.3. Exploratory Objectives

- Evaluate changes in viral loads (CMV, EBV) by qPCR with treatment, where applicable
- Evaluate EBV latency/lytic profile
- Evaluate changes in histone acetylation in PBMCs
- Evaluate immunophenotype and immune function in PBMCs

3. STUDY DESIGN

This is an open-label, 2-part (Phase 1b = dose escalation, Phase 2 = dose expansion) Phase 1b/2 study of VRx-3996 and valganciclovir. The Phase 1b portion of the study will evaluate safety and define a recommended Phase 2 dose (RP2D) using a modified 3+3 design for oncology studies in patients with EBV⁺ lymphomas. The Phase 2 portion of the study will evaluate the RP2D in 30 patients with EBV-associated lymphomas or lymphoproliferative disease, using a Simon's 2-stage design to allow for early stopping for futility. The study defines a cycle length as 28 days. Valganciclovir will be administered at no higher than the approved dose of 900 mg PO BID.

During the Phase 1b portion of the study, dosing will be based on assigned cohort. During the Phase 2 expansion portion, patients will receive the RP2D of VRx-3996 defined previously in the Phase 1b portion of the study. In both phases, patients will continue to receive VRx-3996/valganciclovir if they may still have clinical benefit in the opinion of the Investigator, and in the absence of unacceptable toxicity.

Safety assessments will make use of all available data including using vital signs, physical exams, electrocardiograms (ECGs), PS assessments, and clinical laboratory parameters. Response assessments will be performed using imaging modalities appropriate for the patients' specific lymphoma (e.g., positron emission tomography [PET]-computed tomography (CT), CT scans, magnetic resonance imaging [MRI]) based on the Recommendations for Initial Evaluation, Staging, and Response Assessment of Hodgkin and Non-Hodgkin Lymphoma: the Lugano Classification.²²

Patients considered at risk for tumor lysis syndrome will receive prophylactic medications and interventions.

3.1. Phase 1b (Dose Escalation)

3.1.1. Cohort Size

Cohort size during the Phase 1b portion of the study will be up to 7 patients using a conventional modified 3+3 design for dose escalation studies in oncology. The first cycle (28 days) is defined as the DLT assessment period. At each dose level, 3 or 4 patients will initially be enrolled and followed through the DLT assessment period. If 1 patient in the initial 3 or 4 patients experiences a DLT, the cohort will be expanded to 6 or 7 total patients.

3.1.2. Cohort Enrollment

Enrollment will begin with the Phase 1b portion of the study at the starting cohort as indicated in [Table 5](#).

In the interest of safety, the patient enrollment rate will be limited to no more than 1 patient per week in the starting cohort. The enrollment rate in subsequent cohorts will not be limited.

A patient who experiences clinical benefit while on study treatment, and then experiences progressive disease while not receiving VRx-3996/valganciclovir, may have study drugs restarted if the following conditions are met:

- Restarting study drugs is considered in the patient's best interest by the Investigator,
- The patient has not developed any contraindications to either study drug,
- The Investigator has discussed restarting study drugs with the study Medical Monitor who agrees that restarting of study drugs is appropriate, and
- The study has not been closed by the Sponsor.

The patient should restart study drugs at the RP2D if this dose is tolerated.

3.1.3. Cohort Doses and Regimens

During the Phase 1b portion of the study, the doses of VRx-3996 and valganciclovir will follow those outlined in [Table 5](#). On Cycle 1 Day 1, in an effort to ensure that patients tolerate oral valganciclovir prior to receiving VRx-3996, valganciclovir will be taken first, followed by VRx-3996 approximately 1 hour later. For all subsequent administrations, the sequence of VRx-3996 and valganciclovir can be dictated by patient convenience (e.g., both drugs may be taken together if tolerated by the patient). With the implementation of Protocol Amendment 4.0, VRx-3996 and valganciclovir are taken together at all timepoints, including Cycle 1 Day 1.

The Safety Review Committee (SRC) ([Section 3.10](#)) will have the option of defining additional cohorts and doses either below, above, or intermediate to the doses listed in [Table 5](#) as needed based on data generated from prior cohorts. The SRC may also define additional cohorts based on alternative dosing schedules (e.g., QD versus BID).

Table 5: Phase 1b Cohort Doses

Cohort Number	Dose VRx-3996**	Dose valganciclovir**
1	10 mg BID (20 mg daily dose)	900 mg BID
2a	5 mg BID (10 mg daily dose)	450 mg BID
2b	10 mg QD (10 mg daily dose)	450 mg BID
2c	10 mg QD (10 mg daily dose)	900 mg QD
3	20 mg QD (20 mg daily dose) [#]	900 mg QD

Abbreviations: *BID* = *bis in die* (twice daily); *PO* = *per os* (oral); *QD* = *quaque die* (once daily); *SRC* = Safety Review Committee

** The Schedule used (e.g., *QD*, *BID*) for either VRx-3996 or valganciclovir may be modified by the SRC as required to accommodate different dosage strengths and patient convenience. However, when the schedule is adjusted, the total daily dose will remain unchanged.

In Cohort 3, VRx-3996 will be administered *PO QD* for 4 days on and 3 days off in a 7-day regimen. The dosing holiday is not considered a dosing hold; if a dose is held for any length of time beyond the 3-day dosing holiday (e.g., dosing does not resume on Cycle 1 Day 8), those subsequent days will constitute a dose hold. Please refer to [Section 3.5 Dose Adjustments/Modifications/Delays](#). If the next dose of VRx-3996 following a dosing holiday (e.g., Cycle 1 Day 8) does not coincide with a scheduled visit, the patient should take the next scheduled dose at home.

3.1.4. Dose Escalation Procedure

Dose escalation during the Phase 1b portion of the study will follow commonly accepted criteria used in a modified 3+3 Phase 1 study design.

Dose levels of VRx-3996 and valganciclovir in sequential cohorts will be defined prior to the start of each cohort. If the MTD is exceeded, de-escalation may occur to a lower dose level. Each cohort will initially consist of 3 to 4 patients (See [Section 3.1.1](#)).

If none of the first 3 or 4 patients in a cohort demonstrates a DLT during the first cycle (28 days), then the cohort will be declared safe and the next higher cohort will be opened for enrollment.

If 1 of the first 3 or 4 patients in a cohort demonstrates a DLT during the first cycle (28 days), then an additional 2 or 3 patients will be enrolled to that cohort for a total of 6 patients.

If 1 out of 6 patients in an expanded cohort demonstrates a DLT during the first cycle (28 days), then the cohort will be declared safe and the next cohort will be opened for enrollment.

If 2 or more patients in an expanded cohort demonstrate a DLT, that cohort will be declared to exceed the MTD.

The MTD (if reached) will be defined as the highest dose level at which no more than 1 of 6 patients demonstrates a DLT.

If the MTD is exceeded, then the next lowest dose cohort, or an intermediate dose level (as determined by the SRC) will be expanded to at least 6 patients.

3.1.5. Dose Limiting Toxicity

Grading of DLTs will be according to the National Cancer Institute Common Terminology Criteria for Adverse Events (NCI CTCAE) version 5.

To be considered a DLT, an AE must meet all of the following criteria:

- Occurs during the first cycle (28 days) of study drug administration in Phase 1b only
- Is not incontrovertibly related to underlying disease

In addition, to be considered a DLT, the AE will meet at least one of the criteria listed below:

- Grade 4 anemia unexplained by underlying disease
- Grade 4 febrile neutropenia
- Grade 4 neutropenia lasting >5 days
- Any other Grade 4 hematologic toxicity of any duration
- Grade 4 or higher tumor lysis syndrome
- Grade 3 or higher thrombocytopenia (with or without bleeding)
- Any requirement for platelet transfusion
- Grade 3 or higher non-hematologic toxicity despite adequate supportive care
- Results in a dose hold of >7 consecutive days

Adverse events may be excluded from the definition of DLT if they meet the following criterion:

- AEs that persist <72 hours and are able to be managed with supportive care

The SRC ([Section 3.10](#)) will have the option of declaring other toxicities, not listed above, as DLTs if necessary to ensure patient safety.

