3.1.7. Maximum Tolerated Dose

While this study is not designed to define a MTD for this combination of study drugs, in the event that a DLT is observed, the MTD of VRx-3996 with valganciclovir will be defined as the highest dose administered during Cycle 1 of Phase 1b at which no more than 33% (i.e., ≤ 1 of 6 or 7 patients) experiences a DLT.

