3.2.3. Assessment of Toxicity During Phase 2 Dose Expansion

[figure not shown]
Sequential boundaries will be used to monitor the DLT rate during the dose expansion phase of the study.²⁹ If an excessive number of DLTs are seen, the SRC will have the option of either halting study accrual or reducing the RP2D to reduce the level of toxicity. The boundaries at which the study is halted or the RP2D is reduced are listed in [Table 6](#). This is a Pocock-type

boundary that yields at most a 5% probability of crossing the boundary when the rate of DLT is equal to the acceptable rate of 30%.

Table 6: Early Stopping Boundaries for Toxicity

# Patients	1	2	3	4	5	6	7	8	9	10	11	12	13	14	15
Boundary	-	-	-	4	5	5	6	6	7	7	8	8	9	9	9
# Patients	16	17	18	19	20	21	22	23	24	25	26	27	28	29	30
Boundary	10	10	11	11	12	12	12	13	13	14	14	14	15	15	15

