3.10. Safety Review Committee (SRC)

An SRC will govern the conduct of the study. The SRC will consist of the following individuals appointed by the Sponsor:

- Study Investigators
- The Study Medical Monitor
- A Sponsor representative

Responsibilities of the SRC will include:

- Reviewing study safety data throughout conduct of the study
- Confirming or modifying the specific dose escalations between cohorts
- Defining intermediate dose levels as appropriate
- Declaring the MTD (if reached)
- Determining the RP2D
- Providing guidance on treatment-related issues raised by an Investigator

The SRC will meet at the end of each cohort during the Phase 1b portion and approximately quarterly during the Phase 2 portion, or as needed based on the rate of enrollment.

A Core SRC consisting of 2 investigators and 1 clinical expert appointed by the Sponsor will assess the toxicity during Phase 2 dose expansion ([Section 3.2.3](#)).

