7. SCHEDULE OF EVENTS

The study procedures for the Phase 1b and Phase 2 portions of the study will follow those outlined in [Table 15](#).

Table 15: Schedule of Events

Cycle	SR	1					2		3+		ET	ST	SV
Cycle Day		1	2	8	15	22	1	15	1	15			
Assessment													
Informed consent	X												
Medical history (includes donor data)	X												
EBER/histology sample	X						[X]		[X]		[X]		
Height	X												
Physical examination	X												
Symptom-directed exam		X	X	X	X	X	X	X	X	X	X	X	
Vital signs	X	X	X	X	X	X	X	X	X	X	X	X	
Performance status	X	X	X	X	X	X	X	X	X	X	X	X	
Adverse events		X	X	X	X	X	X	X	X	X	X	X	
Concomitant medications	X	X	X	X	X	X	X	X	X	X	X	X	
Urinalysis	X	X		X	X	X	X	X	X	X	X	X	
Hematology	X	X	X	X	X	X	X	X	X	X	X	X	
Chemistry	X	X	X	X	X	X	X	X	X	X	X	X	
Coagulation	X	X		X	X	X	X	X	X	X	X	X	
Serum pregnancy test	X												
Urine pregnancy test		X					X		X				
12-lead ECG	X	X	X	X	X	X	X	X	X	X	X	X	
Head CT/MRI	X												
Disease assessment	X								X		X		
PK sample(s)		X	X		X		X	X					
Urine PK sample collection		X											
Hepatitis B antigen/antibodies	X												
Hepatitis B DNA PCR	X												
Hepatitis C antibodies	X												
Hepatitis C qPCR	X												

Cycle	SR	1				2		3+		ET	ST	SV
HLA testing		X										
Exploratory Biomarkers												
-Histone H3 acetylation		X	X	X			X					
-Immune profile		X			X		X		X		X	
-EBV and CMV qPCR		X	X	X	X	X	X		X			
VRx-3996/valganciclovir distribution		X					X		X			
VRx-3996/valganciclovir return							X				X	
VRx-3996/valganciclovir compliance assessment		X	X	X	X	X	X	X	X	X		
Survival and follow-up assessment and disease status												X

Study assessments may be performed ± 3 days of the recommended date (however the DLT assessment period should include a full 28 days). Study visits with PK assessments should occur on days that the patient will take both study drugs, VRx-3996 and valganciclovir. End of Treatment (ET) Visit assessments (if needed) will be the same as for the Safety Follow-Up Visit. Safety Follow-Up Visit will be performed 28 ± 7 days after last dose.

SR – Screening (within 21 days of Cycle 1 Day 1)

ET – End of Treatment

ST – Safety follow-up

SV – Survival follow-up contact (performed at least every 3 months after safety follow-up assessment)

X – Required

[X] – Biopsy tissue samples taken per standard of care during study participation and samples taken at the time of relapse should be submitted to the central pathology lab for review.

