4.5.2 Adverse Events

Treatment-emergent adverse events (TEAEs) are defined as those adverse events (AEs) with onset after the first dose of study drug or pre-existing events that worsened by at least one grade after the first dose during the study. Treatment-emergent AEs will be summarized by study phase and cohort. Events reported with a partial onset date (e.g., month and year are reported but the day is missing) will be considered to be treatment-emergent if it cannot be confirmed that the event onset was prior to the first dose of study drug based on the available date entries.

Verbatim terms on case report forms will be mapped to preferred terms and system organ classes using the Medical Dictionary for Regulatory Activities (MedDRA, version 25.0). As an additional safety analysis, certain hematological AEs will be programmatically re-mapped to preferred terms and system organ classes consistent with CTCAE v5.0 categories. Select AE summaries will be repeated using this alternative mapping.

Summaries that are displayed by system organ class and preferred terms will be ordered by descending incidence of system organ class and preferred term within each system organ class. Summaries displayed by preferred term only will be ordered by descending incidence of preferred term. Summaries of the following types will be presented:

- Overall summary of number of unique TEAEs and patient incidence of TEAEs meeting various criteria.
- Overall summary of number of unique SAEs and patient incidence of SAEs meeting various criteria
- Patient incidence of TEAEs by MedDRA system organ class and preferred term
- Patient incidence of TEAEs by CTCAE toxicity grade, MedDRA system organ class, and preferred term.
- Patient incidence of dose-limiting toxicity AEs by MedDRA system organ class and preferred term.
- Patient incidence of TEAEs leading to dose interruption, reduction or discontinuation of valganciclovir by MedDRA system organ class and preferred term.
- Patient incidence of TEAEs leading to reduction or interruption of nanatinostat and valganciclovir by system organ class and preferred term
- Patient incidence of TEAEs leading to discontinuation of nanatinostat and valganciclovir by system organ class and preferred term

- Patient incidence of SAEs by MedDRA system organ class and preferred term.
- Patient incidence of SAEs by CTCAE toxicity grade, MedDRA system organ class, and preferred term.

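### The DLT definition is limited to Phase 1b, so the Phase 2 toxicity stopping boundary in Protocol Table 6 has no event to count

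*Protocol*

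**What the plan says.** Protocol 3.1.5 introduces its first list with "To be considered a DLT, an AE must meet all of the following criteria". The first item on that list is "Occurs during the first cycle (28 days) of study drug administration in Phase 1b only". The second excludes events that are beyond dispute due to the underlying disease. An event must then also meet at least one of the listed toxicity criteria. SAP 3.4.1.1 gives the same definition, with the phase restriction and again as mandatory.

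Protocol 3.2.3, on Phase 2, says "Sequential boundaries will be used to monitor the DLT rate during the dose expansion phase of the study". It gives a Pocock-type boundary for patients 1 to 30 (Table 6), an acceptable DLT rate of 30% and a crossing probability of at most 5% at that rate. On a crossing, the Safety Review Committee (SRC) may halt accrual or lower the recommended Phase 2 dose (RP2D). Protocol 3.10 adds that a Core SRC "will assess the toxicity during Phase 2 dose expansion", with a reference back to 3.2.3.

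Two other places bear on the observation window. Protocol 3.1.1, under the Phase 1b heading, says "The first cycle (28 days) is defined as the DLT assessment period". The footnote to the schedule of events (Table 15), which serves both phases, says "however the DLT assessment period should include a full 28 days". SAP 4.5.2 lists a table of "Patient incidence of dose-limiting toxicity AEs by MedDRA system organ class and preferred term".

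**The concern.** One rule disables another. The stopping boundary exists for Phase 2 and counts DLTs, while the definition of a DLT excludes anything that happens in Phase 2. The word limiting it to Phase 1b is an express exclusion, not a gap that a reader may fill.

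Table 6 is the only numerical toxicity trigger fixed in advance for the expansion phase. If its event is undefined there, the Core SRC must choose for itself what to count: nothing, Cycle 1 events, or events in any cycle. The error rate quoted for the boundary depends on that choice. A choice made after toxicity has been seen in an open-label study is not a prespecified rule.

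Reporting is affected too. Under the SAP definition, the Phase 2 part of the DLT incidence table would be empty whatever happened, and a reader could mistake that for evidence of tolerability, which is a primary objective.

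**Working it through.** **Step 1. Is a Phase 2 DLT defined anywhere?**

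| Place | What it does | Supplies a Phase 2 DLT? |
|---|---|---|
| Protocol 3.1.5, first list | Mandatory; Cycle 1, Phase 1b only | No, excludes it |
| Protocol 3.1.5, SRC clause | Lets the SRC add toxicities that are not on the list | No; it adds event types and leaves the phase condition in place |
| Protocol 3.1.1 | Sets Cycle 1 as the DLT period, under the Phase 1b heading | No |
| Protocol 3.2.3 and Table 6 | Boundary on the DLT count in Phase 2 | No; uses the term without defining it |
| Protocol 3.10 | Gives Phase 2 toxicity to the Core SRC | No |
| Protocol Table 15 footnote | Asks for a full 28-day DLT period | Suggests a window, defines no event |
| SAP 3.4.1.1 | Repeats 3.1.5 | No, excludes it |
| SAP 3.1.2 and 4.6.5.3 | Core SRC assesses toxicity; no boundary, no event | No |

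Literally, then, the Phase 2 count is 0 for every patient.

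**Step 2. Does Table 6 do what the protocol says when events do count?**

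Inputs, all from Protocol 3.2.1 and 3.2.3: 30 patients; acceptable rate 30%; no boundary for patients 1 to 3; for patients 4 to 30 the boundaries 4, 5, 5, 6, 6, 7, 7, 8, 8, 9, 9, 9, 10, 10, 11, 11, 12, 12, 12, 13, 13, 14, 14, 14, 15, 15, 15.

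Let P(n, k) be the probability of k DLTs among n patients with no earlier crossing, starting from P(0, 0) = 1. For true rate p,

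P(n, k) = (1 − p) · P(n − 1, k) + p · P(n − 1, k − 1).

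After each patient, all mass with k at or above the boundary for n is moved to crossed. The crossing probability is the total moved by n = 30.

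At p = 0.30 this gives 0.0494, so the protocol's ceiling of 5% reproduces. The table also rebuilds exactly in all 30 entries as the smallest r with Pr(Bin(n, 0.30) ≥ r) ≤ 0.0171. For example, Pr(Bin(4, 0.30) ≥ 4) = 0.3⁴ = 0.0081, and Pr(Bin(30, 0.30) ≥ 15) = 0.0169. With three patients, 0.3³ = 0.027 exceeds 0.0171, which is why the first three entries are blank.

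**Step 3. What the trigger would do, against what it does as written.** Expected numbers assume that a crossing halts accrual and that each Cycle 1 outcome is known before the next patient starts.

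| True DLT rate | P(cross), Cycle 1 events in Phase 2 count | Expected patients treated | P(cross), definition as written | Patients treated, as written |
|---|---|---|---|---|
| 20% | 0.0045 | 29.9 | 0 | 30 |
| 30% | 0.0494 | 29.2 | 0 | 30 |
| 40% | 0.2605 | 26.4 | 0 | 30 |
| 50% | 0.6503 | 20.7 | 0 | 30 |
| 60% | 0.9268 | 14.1 | 0 | 30 |

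**Step 4. Effect of accrual lag.** The documents give no accrual rate. Assume 4 to 8 further patients start before a halt takes effect, capped at 30 in total. The expected number treated becomes 27.3 to 28.1 at 40%, 23.1 to 25.1 at 50% and 17.7 to 21.0 at 60%. The crossing probabilities do not change.

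**The case against.** The strongest reply is that no committee would read the text this way. Section 3.1.5 sits under the Phase 1b heading, 3.2.3 is the specific rule for Phase 2, and the Core SRC would simply apply the listed toxicities. That is probably the intent, and it makes 0% a statement about the text, not a forecast of conduct. But intent does not settle which events count or over what period.

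A second reading attaches the restriction to the window: Cycle 1 limits apply in Phase 1b, and Phase 2 toxicities count at any time. The sentence that makes every item mandatory tells against this. That the reading can be argued at all shows that the window needs to be written down.

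Third, a crossing gives the SRC a choice between halting and lowering the dose, and a halt would come with a lag. This stands as a limit on the expected numbers in Step 3, and Step 4 shows the range. It does not touch the crossing probabilities.

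Fourth, the SRC reviews safety throughout, may change the RP2D (Protocol 3.2.2), and patient-level dose holds apply (5.1.8). Phase 2 toxicity is also tabulated by grade, seriousness and dose modification (SAP 4.5.2). All of this stands, and so Phase 2 is not unguarded. These measures are either discretionary or act on single patients, and none replaces a prespecified trigger at study level.

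**Conclusion.** The concern holds. As written, the DLT definition in Protocol 3.1.5 and SAP 3.4.1.1 switches off the Phase 2 boundary in Protocol 3.2.3, and nothing else in either document restores it. The boundary values are correct and meet the stated 5% limit; the fault lies only in the event they count.

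The size of what is lost is the gap between 0% and a crossing probability of 26%, 65% or 93% at true DLT rates of 40%, 50% or 60%. This assumes a Cycle 1 window, independent outcomes, crossing when the count reaches the boundary, and 30 patients. The saving in patients treated rests further on a halt being chosen and on how quickly outcomes are known. Because a safety stopping rule is disabled by its own definition and the repair is small, this should be fixed before the rule is relied on and before the DLT table is produced.

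**What to change.** Make one of two changes.

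- Delete the restriction to Phase 1b from Protocol 3.1.5 and SAP 3.4.1.1, leaving the first 28-day cycle as the window in both phases. The Phase 1b rules are not disturbed: 3.1.6 is itself limited to Phase 1b, and 3.1.7 refers to "the highest dose administered during Cycle 1 of Phase 1b".
- Or keep the definition and state in Protocol 3.2.3 and in the SAP that, for Table 6, the toxicity criteria of 3.1.5 apply to Cycle 1 (28 days) of Phase 2.

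The second is the more explicit, because it names the window next to the rule that uses it. Both fix a Cycle 1 window. If the sponsor wants later toxicities to count, that has to be said, and the 30% acceptable rate justified again for the longer period. In either case, state that the SAP's DLT incidence table includes Phase 2.

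The cost is a phrase or sentence in each document, plus the ethics review that any amendment needs under Protocol 16.2. No new assessments are required, since adverse events are already collected at every Cycle 1 visit in both phases, and Table 6 stays as it is.
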